4.3.4. Work plan and data collection

TASKS	YEAR 2020					Responsible units
	1	2	3	4	Months Successive	
Design version 1.0, CI approval, CEIm, communication to the AEMPS, application for financing	x					Haematology, Internal Medicine, Intensive Medicine, Research Unit, Microbiology
Obtaining IdISBa financing		x				Haematology, Internal Medicine, Research Unit
Revision version 1.0, writing version 2.0 (multicentre study)			x			Haematology, Internal Medicine, Research Unit
Commissioning		x				Haematology, Internal Medicine, Intensive Medicine, Research Unit, Microbiology
Patient Recruitment		x	x	x	x	Haematology, Internal Medicine,
Experimental phase		x	x	x	x	Haematology, Internal Medicine, Intensive Medicine, Microbiology, Clinical Analysis
Data collection		x	x	x	x	Coordination of Haematology trials
Data analysis			x	x	x	Research Unit
Dissemination of results			x	x	x	Haematology, Internal Medicine, Intensive Medicine, Research Unit

Table 2. Schedule of the phases of the study.

5. DATA ANALYSIS: STATISTICS

A descriptive analysis of all variables will be performed. With the categorical variables, the global percentages and frequencies will be estimated. Normality tests and graphs will be used to determine if the quantitative variables follow a normal distribution. Normal distribution variables shall be expressed as mean \pm standard deviation and those without normal distribution shall be expressed as median and interquartile range. To describe the significance and associations between variables after the intervention, parametric and non-parametric tests will be used as appropriate (the student's t test of paired samples or the Wilcoxon test for quantitative variables and the ANOVA test for paired samples or Friedman test for qualitative variables). The correlations will be examined by the correlation of Spearman or Pearson ranges and a multivariate analysis will be performed to assess the effect of other factors such as the confusion/interaction effect, as well as to assess the possible construction of predictive models. A p-value $< 0,05$ shall be considered an indicator of a significant difference. SPSS v.23 software will be used for data analysis.

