3.2. Objectives

3.2.1. Main objective:

The objective of the study is to determine the efficacy of reinforcing standard treatment with repeated infusions of plasma from people ex-convalescent of COVID-19 disease (already discharged and/or with negative COVID-19 test results), transfused to COVID-19 patients still hospitalized, both COVID-19 plant and HUSLL ICU ([and collaborating centres participating in the multicentre study](#)). Comparing it with the results obtained with the exclusive use of standard treatment, which is being used in patients infected with COVID-19. Therefore, to assess the immunological efficacy of the reinforcement of standard treatment vs standard therapy without reinforcement.

3.2.2 Secondary objectives:

Secondary objectives are related to evaluating not only efficacy at the clinical level, but also tolerance, safety and immunological aspects. Below is a list of the main secondary objectives:

- To assess the serological response to Coronavirus SARS-CoV-2 in patients with plasma transfusion and compare it with patients who have received treatment standard.
- Analyse the influence of the number of antibodies of the donor on the clinical evolution of the recipient.

-Analyse the efficacy of the experimental treatment that will reinforce the standard treatment, comparing it with the exclusive standard treatment at the level of the main clinical parameters during and after the treatment.

-To assess the safety of experimental reinforced treatment, comparing it with standard treatment during and after treatment.

-To assess the tolerance of experimental reinforced treatment, comparing it with standard treatment during and after treatment.

-Evaluate the feasibility of the experimental reinforced treatment.

-To assess the virological response of patients with plasma transfusion versus patients with standard treatments.

-Find if there is a certain patient profile where this therapy is most effective, either by age group, blood group, sex, or presence/absence of other pathologies.

-On the contrary, determine if there is a certain profile of patients (as in the previous case) in which the treatment is less effective.

-To know retrospectively the parameters of antigenemia and viral load of convalescent patients infected by COVID-19.

-Find possible weak points of experimental therapy that need to be studied to be improved in future studies.

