4. STUDY DESIGN

4.1. Type and design of the study Pilot study of phase I, open, two-branch, **multicentre** clinical trial for the study of the efficacy of passive immunization through repeated infusion of plasma from people exvalescing from infection with COVID-19 and/or with a negative viremia result for COVID-19, together with the standard treatment that is currently being scheduled, compared to the exclusive application of standard treatment in currently hospitalized COVID-19 patients. **The study will be carried out and coordinated by HUSLL, which may be joined by all health centres interested in participating in the study that meet the requirements to be able to develop it and commit to the conditions of the same. In each centre, the study subjects will be selected among those admitted to both the COVID-19 plant and the ICU (or their counterpart places in each centre).** Below is an outline of the study design:

[figure not shown]

Fig 1. Outline of the design of the study protocol to be carried out.

IMPORTANT NOTE: the scheme refers to the coordinating centre (HUSLL), but the same conditions are extended to all those centres participating in the multicentre study.

The assignment to the control and intervention groups, both in the plant and in the ICU, will be done by means of simple random assignment, using equiprobability calculations through a computer system, in order to guarantee that all subjects have the same probability of belonging to the two groups. The system will be the same in all participating centres. This system will be carried out whenever a plasma stock is available. In the event that the stock runs out, the recruited patients will be part of the control group.

The characteristics of the experimental groups are detailed below:

-For intervention group: usual standard treatment (according to clinical guideline for COVID-19), plus two infusions followed by a volume equal to 300 ml of plasma from patients convalescing from COVID-19 and with negative viremia in the COVID-19 detection test and therefore discharged and / or cured. The infusions will be given on days 1 and 2 of study, after the positive result for COVID-19 of the recipient patient, who will be treated.

-For control group: usual standard treatment, according to clinical guideline for COVID-19. This is based on any drug used in clinical practice accepted to date, from retroviral (lopinavir/ritonavir;

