darunavir/cobicistat; remdesivir), interferon- α/β , anti-IL-6 monoclonal antibody (Tocilizumab) or oxygen therapy among others. The ratio controls: treated will be 1:2 in favour of the treatment. As treatments have been changing throughout the pandemic, when performing the final analysis, a stratified analysis will be made by type of treatment. That is, infected patients who have been treated with the same drugs will be compared.

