4.2.3. Patient withdrawal criteria

The patient will be removed from the study when any of the following circumstances are met:

- Patients who have not had both plasma infusions.
- Unacceptable toxicity.
- Withdrawal of the IC.
- Completion of the study.
- Exitus.

Patients will be informed that they can leave the study at any time without affecting their medical care in the future. The reason and date of departure of the study will be recorded in the patient's medical history.

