4.3.2. Duration of the study

In version 1.0 of the study, the estimated study duration period was 3 months from the date of compliance with the Clinical Research Ethics Committee (in Spain CEIm) Research Ethics Committee (CEIm) and Spanish Agency for Medicines and Health Products (in Spain AEMPS). In this version 2.0 the study period is extended to recruit a sufficient n to be able to estimate the effectiveness of the treatment or failing that until the competent authorities so determine. The follow-up period for patients will be 21 days from the start date of the study and if necessary, it will be extended as long as necessary, in order to ensure patient safety.

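### The main objective compares plasma with standard treatment, but section 5 names only within-patient tests for differences and no between-arm test or model with a stated arm term

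*Combined protocol and SAP*

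**What the plan says.** Section 3.2.1 sets the main objective as the efficacy of adding plasma to standard treatment: "Comparing it with the results obtained with the exclusive use of standard treatment". The safety objective in section 3.2.2 is also comparative: "To assess the safety of experimental reinforced treatment, comparing it with standard treatment during and after treatment".

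Section 4.1 describes two branches filled by "simple random assignment, using equiprobability calculations through a computer system", with a stated control-to-treated ratio of 1:2 and no matching. It adds an exception to randomisation: "In the event that the stock runs out, the recruited patients will be part of the control group". It also promises a final analysis stratified by background treatment, in which "infected patients who have been treated with the same drugs will be compared", but names no test, model or outcome.

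Section 5 gives descriptive statistics and then, for testing after the intervention, lists the Student t test for "paired samples or the Wilcoxon test for quantitative variables and the ANOVA test for paired samples or Friedman test for qualitative variables". It goes on to Pearson or Spearman correlations, a multivariate analysis of other factors including confounding and interaction, possible predictive models, and a 0.05 threshold for a significant difference. Arm, group and control are not mentioned.

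**The concern.** The question the trial asks and the tests the plan names do not match. The question is whether two groups of different patients differ. The named tests ask whether the same patients differ between time points. A paired test in the plasma arm uses no control data, so its p-value is the same whether controls did worse, equally well or better.

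There is a second mismatch. Paired ANOVA and Friedman are assigned to qualitative variables. Neither can analyse an outcome recorded once per patient, such as death or ICU admission. Friedman can be used on repeated RT-PCR, ECOG or WHO scores, but it then tests change over time and not a difference between arms.

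Unless the unspecified multivariate model contains arm, no specified p-value addresses the main objective. Ordinary recovery during follow-up could be reported as a plasma effect. In an open-label trial, choosing the between-arm test after seeing the data would weaken any result.

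**Working it through.** **1. Reading the text.** Each test that section 5 names for differences, with what it compares:

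| Named test | Compares | Uses control data to judge plasma? |
|---|---|---|
| Paired t | Two times, same patients | No |
| Wilcoxon, as its alternative | Two times, same patients (signed-rank) | No |
| Paired-samples ANOVA | Several times, same patients | No |
| Friedman | Several times, same patients | No |

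Section 5 contains no independent-samples t test, Mann-Whitney, chi-square, Fisher, log-rank or ANCOVA, and no regression with a treatment term.

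**2. Illustration of the consequence.** The plan gives no sample size, SD or expected change, so there is no figure of its own to reproduce. Every input below is an assumption: 20 or 40 plasma patients; a true mean change d of 0.3, 0.5 or 0.8 SD of the change score, the same in both arms; no plasma effect; two-sided 0.05.

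The rejection probability of the paired t test is P(|T| > t crit), where T is noncentral t with n − 1 degrees of freedom and noncentrality d√n.

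| n (plasma) | t crit | d = 0.3 | d = 0.5 | d = 0.8 |
|---|---|---|---|---|
| 20 | 2.093 | d√n = 1.342: 24.7% | 2.236: 56.5% | 3.578: 92.4% |
| 40 | 2.023 | d√n = 1.897: 45.7% | 3.162: 86.9% | 5.060: 99.9% |

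A between-arm t test on the same null scenarios (40 versus 20, following the 1:2 ratio; 60,000 simulated trials) rejects in 5.1%, 5.0% and 4.8%.

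If controls instead improve by 0.8 SD while plasma patients improve by 0.5 SD, so that plasma patients do worse, the plasma-arm paired test still rejects in 86.9% of trials at n = 40. The control data never enter the calculation.

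Reading the two arms' paired tests side by side does not repair this. With no plasma effect and 40 versus 20 patients, the plasma arm is significant and the control arm is not in 34.5%, 38.0% and 7.3% of trials for the three values of d (20,000 simulations).

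**3. RT-PCR.** The schedule has five tests: baseline and days 3, 7, 14 and 21. Assume positivity of 100, 95, 90, 85 and 80% in both arms, with no return to positive. Friedman (Cochran's Q for binary data) gives p<0.05 in 66% of 20-patient arms and 98% of 40-patient arms (20,000 simulations). Fisher's exact test between arms at day 21, with 80% positive in both and 40 versus 20 patients, rejects in 3.5% (exact).

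**4. A limit on the 5%.** The between-arm error rate holds only if the controls are comparable. Take 40 plasma patients and 20 randomised controls, all changing by 0.5 SD, and pool in stock-out controls whose mean change differs by 0.3 or 0.5 SD. With 10 added, the t test rejects in 6.9% or 10.0%; with 20 added, in 9.7% or 18.8% (100,000 simulations). With randomised controls only, it stays at 4.9% to 5.2%.

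**The case against.** The best reply is that a between-arm analysis is implied. Confounding and interaction only make sense relative to an exposure, so the multivariate analysis probably contains arm. Section 4.1 promises a comparison within background-drug strata. Section 5 says tests will be chosen as suits the data, and its Wilcoxon is unqualified, so it could be the rank-sum test. This is also a phase I pilot with no sample-size calculation.

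The intention to compare is fairly inferred, and an arm term may well have been meant. But no outcome, model type or arm term is written down, and the stratified comparison has no method. The latitude is followed by a list of paired procedures only. Wilcoxon appears there as the alternative to the paired t test, next to Friedman; even read as rank-sum it would cover quantitative variables only, leaving death, ICU admission, RT-PCR status and adverse events with no between-arm test. Pilot status does not settle it either, since efficacy against standard treatment is the stated aim and section 5 sets a significance threshold.

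Three narrower objections stand:

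- Table 1 has no arm variable and gives adverse-event incidence for the experimental branch only, but this is weak evidence. The table is not exhaustive. Annex IX assigns the branch, the Annex V form has a randomisation field, and adverse events are reviewed in both groups at every visit. The data for a comparison are planned; the method is missing.
- The percentages are the power of a paired test at chosen changes. They become false claims of efficacy only if a plasma-arm p-value is read as proof.
- The stock-out calculation concerns who is analysed, which is a separate question from paired versus independent tests.

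**Conclusion.** The concern holds and should be settled before any analysis. For differences, section 5 names only within-patient tests, and no between-arm test or model with a stated arm term is specified anywhere for the main comparison. This is more than missing detail: carrying out the listed tests as written would answer a different question.

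The textual finding rests on reading Wilcoxon as signed-rank, which its place in the list supports. The size cannot be derived from the documents. Under the assumed sizes and changes, the plasma-arm paired t test is significant in 25% to over 99% of trials when plasma does nothing, against about 5% for a between-arm test in comparable randomised groups. The exact percentages move with the assumptions; the mechanism does not.

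**What to change.** Replace the test sentence in section 5 with a named between-arm analysis for each outcome type. Reasonable options are:

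- **Quantitative** (such as antibody titre): baseline-adjusted ANCOVA or a mixed model with an arm term; rank-sum if skewed.
- **Binary** (death, RT-PCR at a stated visit, adverse events by arm, and ICU admission among ward recruits only): Fisher or chi-square, or logistic regression.
- **WHO scale and ECOG**: rank-sum or proportional odds. Table 1's WHO coding has no death level, so deaths need the worst rank; ECOG already codes death as 5.
- **Time to RT-PCR negativity and to discharge**: a time-to-event comparison with death as a competing event.

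State that the multivariate model contains arm, and keep the paired tests as within-arm description.

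Two secondary points protect the comparison. Base it on patients randomised while plasma was available, analysed as randomised, and report stock-out controls separately. Keep in the analysis the outcomes of those removed under section 4.2.3, which lists "Patients who have not had both plasma infusions" as well as death. Where numbers allow, adjust for ward or ICU and carry out the promised same-drug comparison.

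The cost is one rewritten paragraph, plus arm and assignment route (randomised or stock-out) in Table 1, as a written amendment approved before use under section 6.1. Setting stock-out controls apart also changes how section 4.1's control group enters the analysis, and the amendment should say so. Arm is already known, and no new patient procedure is needed. Three practical limits apply:

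- Section 4.3.2 says "The follow-up period for patients will be 21 days from the start date of the study", extendable for safety, while Table 1 lists 30-day mortality. Where 30-day status is not obtained, use 15-day mortality or death by day 21.
- The WHO score needs a stated visit, because the schedule shows only a clinical response row.
- Outcomes must still be collected for patients removed for a missed infusion.

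The amendment would not by itself name a primary outcome. Section 4.3.3 marks none, which is a separate gap.

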- Quantitative determination of antibodies (IgG, IgM) against Coronavirus SARS-COV-2.
- Concomitant medication evaluation
- Evaluation of emerging adverse effects.
- Clinical/virological response evaluation.

6. Visit of Day 14:

- Vital signs (TA, FC, FR, T^a).
- Physical examination.
- Hematimetry.
- Biochemical analysis.
- Nasal and pharyngeal smear for RT-PCR of Coronavirus SARS-COV-2.
- Quantitative determination of antibodies (IgG, IgM) against Coronavirus SARS-COV-2.
- Concomitant medication evaluation.
- Evaluation of emerging adverse effects.
- Clinical/virological response evaluation.

7. Visit of Day 21/end of study (at discharge):

- Vital signs (TA, FC, FR, T^a).
- Physical examination.

- Rx of Tx to assess evolution/resolution of infiltrates.
- ECG.
- ECOG.
- Hematimetry.
- Biochemical analysis.
- Inflammatory parameters.
- Real Time-PCR for SARS-COV-2 viral load study.
- Quantitative determination of antibodies (IgG, IgM) against Coronavirus SARS-COV-2.
- Concomitant medication evaluation.
- Evaluation of emerging adverse effects.
- Clinical/virological response evaluation.

IMPORTANT: In cases where the patient is discharged after 7 days, visits on day 14 and day 21 can be made on an outpatient basis, in outpatient consultations or day hospital, after appointment with the patient.

Screening visits and day 1 may overlap on the same date threaten life the inclusion criteria are confirmed and none of the exclusion is met.

There will be a margin of +/- 24 hours to perform the procedures of visits 7, 14 and 21 (to be able to adjust the appointments in external consultation).

The study procedures for study subjects (control and treatment groups) can be reviewed in summary form in the following table:

Procedure	Study days						
	Screening/ Basal	Day 1*	Day 2	Day 3	Day 7	Day 14	Day 21
DATE							
Signature of informed consent	X						
Medical history review	X						
Physical examination	X	X*		X	X	X	X
Vitals signs	X	X*		X	X	X	X
Weight, Height, BMI	X						
ECOG	X	X*		X	X	X	X
ECG	X				X		X
ABO/Rh Group	X						
Hematimetry	X	X*		X	X	X	X
Coagulation	X	X*		X	X	X	X
Biochemistry	X	X*		X	X	X	X
Study of inflammatory parameters	X			X	X		X
Serology Important IgG/IgM anti-COVID	X			x	x	x	x
Quantitative titration antibodies	X			X	X	X	X
COVID PCR	X			X	X	X	X
Chest Rx	x						x
AE Review	X	X	X	X	X	X	X
Concomitant review	X	X	X	X	X	X	X
Clinical response	X			X	X	X	X
PLASMA TRANSFUSION		X	X				

Table 3. Summary of procedures in the study subjects.

LEGEND:

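### Section 5 names only within-patient tests for repeatedly measured outcomes, with no baseline-adjusted arm comparison and no rule for missed visits or death

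*Combined protocol and SAP*

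**What the plan says.** **Tests.** Section 5 is the whole statistical plan. For quantitative variables it names "the student's t test of paired samples or the Wilcoxon test for quantitative variables"; for the rest it names "the ANOVA test for paired samples or Friedman test for qualitative variables". A p-value below 0.05 "shall be considered an indicator of a significant difference". It adds that "a multivariate analysis will be performed to assess the effect of other factors such as the confusion/interaction effect". Section 4.1 adds a final analysis stratified by type of standard treatment, without naming a model. No missing-data rule, analysis set or treatment of death is given.

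**Schedule.** Section 4.3.1 and its Table 3 place haematology, biochemistry, RT-PCR, "Quantitative determination of antibodies (IgG, IgM) against Coronavirus SARS-COV-2" and "Clinical response" at screening and on days 3, 7, 14 and 21. Inflammatory parameters are taken on days 3, 7 and 21. ECOG on day 14 is marked in Table 3 but is absent from the day-14 visit list. After discharge, "visits on day 14 and day 21 can be made on an outpatient basis".

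**Who stays in.** Section 4.2.2 lists, among the ward recipients' exclusion criteria, not having completed all study procedures. Section 4.2.3 removes patients from the study on death or if they did not receive both infusions.

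**Death in the scales.** In Table 1 (section 4.3.3) ECOG has a code for death, 5. The WHO progression scale as tabulated runs from 0 to 9 with no death level.

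**The concern.** The main objective is a comparison of plasma plus standard treatment with standard treatment alone. Ward patients (SOFA of 6 or less) and ICU patients (SOFA above 6) are enrolled together under simple random assignment. Baseline values will therefore vary widely, and chance imbalance between arms is plausible. A patient's own baseline is then likely to be a useful covariate, and the plan collects it. Yet the named tests use baseline only as the other half of a within-patient pair and yield no adjusted arm difference.

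Two things are at stake. The first is precision, in a trial with no fixed sample size (section 4.2.10) and a plasma supply that can run out (section 4.1). The second is who is analysed. Tests that need complete blocks keep patients who survived and attended every visit. Gaps are foreseeable, since days 14 and 21 may be outpatient visits, and deaths are to be expected in an ICU stratum. The rules in sections 4.2.2 and 4.2.3 push the same way, before any test is run.

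**Working it through.** The plan states no sample size, power, effect, standard deviation, correlation or dropout rate, so there is no figure of its own to reproduce. The values of p, r and the effect size below are assumptions, shown as ranges where they drive the result.

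**1. What each named test needs**
- Paired t and Wilcoxon need the two values being compared. A missed day 14 does not remove a baseline-to-day-7 pair.
- Paired-samples ANOVA in its classical form and Friedman need a value at every visit analysed. One gap removes the patient from that test. Section 5 assigns these to the variables it calls qualitative.

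**2. Complete-block loss (ANOVA and Friedman only)**

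Let p be attendance per later visit, assumed independent across visits, with baseline always present. The fraction complete over k later visits is p^k; k = 4 for days 3, 7, 14 and 21.

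| p | one pair | p^3 | p^4 |
|---|---|---|---|
| 0.95 | 95% | 85.7% | 81.5% |
| 0.90 | 90% | 72.9% | 65.6% |
| 0.85 | 85% | 61.4% | 52.2% |

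The p^3 column applies to ECOG if the day-14 visit list, rather than Table 3, is followed.

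**3. Precision of an arm comparison**

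Let r be the correlation between baseline and follow-up, with equal variances. Relative to an unadjusted follow-up value, the variance of the arm difference is 2(1 − r) for change scores and 1 − r² with baseline as a covariate. The ratio is 2(1 − r)/(1 − r²) = 2/(1 + r), whatever the allocation ratio.

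| r | change score | baseline-adjusted | ratio | extra patients |
|---|---|---|---|---|
| 0.3 | 1.40 | 0.91 | 1.54 | 54% |
| 0.5 | 1.00 | 0.75 | 1.33 | 33% |
| 0.7 | 0.60 | 0.51 | 1.18 | 18% |

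For scale, take an assumed effect of 0.5 SD, two-sided 5%, 80% power and the ratio in section 4.1 ("The ratio controls: treated will be 1:2 in favour of the treatment"). Controls needed are 1.5 × (1.96 + 0.84)² × variance / 0.5², about 47.1 × variance, and the total is three times the rounded-up number. At r = 0.3, 0.5 and 0.7, change scores need 198, 144 and 87 patients; baseline adjustment needs 129, 108 and 75.

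**4. RT-PCR**

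A positive PCR is an entry requirement (section 4.2.1), so baseline RT-PCR offers nothing to adjust for. The argument in step 3 does not apply to it.

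**The case against.** The strongest reply has four parts.

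- **The multivariate analysis might include baseline.** That is possible, so a reader cannot conclude that the plan as a whole will never adjust. But the sentence names no outcome, model or covariate, so it commits the trial to nothing.
- **The plan never compares arms on change scores.** This is correct. The 54%, 33% and 18% are the price of one obvious way of turning the named paired tests into an arm comparison; they are not a cost of anything section 5 states.
- **Most listed outcomes are quantitative.** A reader might infer that any missed visit removes a patient from every analysis. The documents do not support that: laboratory values, antibody titres and inflammatory markers fall under the paired t or Wilcoxon test, which lose only a pair. The complete-block loss stands for ANOVA and Friedman alone.
- **Survivor bias is not demonstrated.** A reader might infer that the comparison is biased towards survivors by a known amount. A distortion between arms needs loss that differs by arm or is related to the treatment effect, and the documents give no death or attendance rates from which to size it. ECOG could also retain deaths through its code 5, although nothing says it will.

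It can also be said that the more basic fault is the absence of any named between-arm test. That is true, but adding one on change scores or on complete cases would leave the present point in place.

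**Conclusion.** The point holds as a gap in specification. For outcomes measured at baseline and up to four later visits, section 5 names only within-patient tests. It fixes no baseline-adjusted arm comparison and has no rule for missed visits or death.

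The sizes are conditional. Complete-block retention of 81%, 66% or 52% rests on assumed independent attendance and concerns only the variables given ANOVA or Friedman. The 18% to 54% penalty rests on assumed correlations and on an arm comparison the plan does not state. No size can be given for survivor selection. The change is worth making because it uses data already scheduled, in a trial that cannot count on a large sample.

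**What to change.** Amend section 5 so that the arm comparison is:

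- **Quantitative outcomes:** a linear mixed model on all available visits (log scale for skewed markers) with arm, visit, arm-by-visit and the patient's own baseline value. A mixed model does not itself resolve death, so report deaths by arm alongside it.
- **Ordinal outcomes (ECOG, WHO scale):** a proportional-odds model with baseline level as covariate and death as the worst category. ECOG already has that code; add a death level for the analysis of the WHO scale as tabulated.
- **RT-PCR:** a logistic GEE with arm and visit, without baseline RT-PCR.

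Keep the paired tests as within-arm description. Define the analysis set as all assigned patients, and reconcile with it the incomplete-procedures criterion in section 4.2.2 and the removal rules in section 4.2.3; a new model cannot recover patients removed before it is fitted. Settle whether ECOG is taken on day 14.

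**Cost:** a written protocol amendment, which section 6.1 requires to be approved before implementation, and modest analysis work. No new data are needed.
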